8.2.4 Possible Interactions with Concomitant Medical Treatments

Subjects participating in the investigation will be provided with a card advising of the contraindication of magnetic resonance imaging (MRI), and providing contact information of the investigational site.

Subjects must not undergo MRI while the Sensor is inserted or the Transmitter is in place. Both are incompatible with MRI procedures. Serious injury such as internal tissue burn (from the Sensor overheating) or topical skin burn (from the Transmitter overheating) may occur during an MRI and subsequent localized infection may develop as a result of the Sensor overheating.

If an MRI is required for subject care, the Sensor should be removed and the Subject will be withdrawn from the study, according to study stopping rules.

In the event of a situation where MRI is required and it is not possible to remove the Sensor, Subject is advised to have medical staff contact the Sponsor.

8.2.5 Dexamethasone

As it has not been determined whether the risks usually associated with injectable dexamethasone apply to the use of dexamethasone elution ring, a highly localized, controlled-release device, routine blood dexamethasone measurements have been incorporated into the study design.

8.2.6 Electrostatic Shock

The external device (Transmitter) has been tested and passed the Electrostatic Discharge (ESD) test according to IEC 61000-4-2:2008 air and contact immunity test levels in accordance with IEC 60601-1-2:2014 EMC collateral standard. No known damage to the external device or to the overall CGM system has been observed as documented in the EMC report.

8.3 Efforts to Minimize Risk

This investigation will be conducted by investigators who are qualified by training and experience in the treatment of diabetes mellitus and specifically in the execution of hyperglycemia and hypoglycemia challenges. In the event of a clinical emergency, detailed safety plans will be in place at each clinical site for monitoring and the management of clinically significant hypoglycemia and hyperglycemia. A full resuscitation cart with defibrillator, and staff trained in the care of diabetes and cardiac emergencies will be present at site. A nurse, nurse practitioner or physician will be present at the bedside or unit at all times. A study physician or nurse practitioner will be present during the hypoglycemia and hyperglycemia challenge times.

In addition, adequate measures including eligibility criteria limitations, subject screening and pre-visit assessment of the subject's diabetes status have been incorporated into the clinical investigation with the intention of minimizing such risks.

Investigators will be trained in the technique for Sensor insertion and removal. Investigators will examine the insertion site during each in-clinic visit and document any suspected adverse event. Subjects will be instructed to contact the investigator immediately upon any sign of significant irritation or discomfort or evidence of infection as described previously. In addition, an independent medical monitor will review safety related aspects of the investigation including review of serious adverse events and unanticipated adverse device effects.

Furthermore, potential risks associated with participation in this investigation will be minimized and managed in accordance with 21 CFR Part 812, ISO 14155, regulations by local regulatory authorities and requirements of the approving Investigational Review Boards and Ethics Committee(s).

8.4 Risk to Benefit Ratio

The Sponsor believes that any potential risk presented by this investigation has been minimized and that adequate testing, safeguards, and safety monitoring have been incorporated into the investigation to further minimize and mitigate the risks.

The Sponsor believes that the value of the knowledge to be gained by conducting this clinical investigation to demonstrate the safety and accuracy of the Senseonics CGM System outweighs the potential risks posed to participating subjects.

All potential study Subjects will sign an informed consent form and conduct a discussion with delegated investigative personnel concerning the risks and benefits of participating in the clinical trial.

9 ADVERSE EVENTS

The following are definitions and requirements for adverse event monitoring and reporting. The definitions and requirements of local regulations will be followed if different from below.

The name and telephone number of the individual for the Site to contact regarding safety issues is listed in the General Information and Contacts section in the front of the protocol. Subjects will contact the Investigator with any questions or concerns. The Investigator will contact Senseonics with questions regarding recording and reporting of adverse events.

9.1 Adverse Event Definitions

Adverse Event (AE) is defined as any untoward medical occurrence, unintended disease or injury, or untoward clinical signs (including abnormal laboratory findings) in subjects, users or other persons, whether or not related to the investigational medical device.

NOTE 1 This definition includes events related to the investigational medical device or the comparator.

NOTE 2 This definition includes events related to the procedures involved.

NOTE 3 For users or other persons, this definition is restricted to events related to investigational medical devices.

Serious Adverse Event (SAE) is defined as an adverse event that:

- Leads to death;
- Leads to a serious deterioration in the health of the Subject that either:
 - Results in life-threatening illness or injury; or
 - Results in a permanent impairment of a body structure or a body function; or
 - Requires inpatient or prolonged hospitalization; or
 - Results in medical or surgical intervention to prevent life-threatening illness or injury or permanent impairment to a body structure or a body function;
- Led to fetal distress, fetal death or congenital abnormality or birth defect;
- Significant medical event.

NOTE: Planned hospitalization for a pre-existing condition, or a procedure required by the CIP, without serious deterioration in health, is not considered a serious adverse event.

Anticipated adverse events are AEs that have been identified as possible adverse events related to the investigational device or procedure.

Unanticipated adverse device effects (UADEs) are defined as any serious adverse effect on health or safety or any life-threatening problem or death caused by, or associated with, a device, if that effect, problem, or death was not previously identified in nature, severity, or degree of incidence in the investigational plan or application (including a supplementary plan or application), or any other unanticipated serious problem associated with a device that relates to the rights, safety, or welfare of study subjects.

Severity

Mild: Awareness of a sign or symptom that does not interfere with the Subject's usual activity or is transient, resolves without treatment and with no sequelae

Moderate: Interferes with the Subject's usual activity and/or requires symptomatic treatment

Severe: Symptom(s) causing severe discomfort and significant impact on the Subject's usual activities and/or requires treatment

Causality: The causal relationship should be determined with respect to the investigational device, the insertion or removal procedure, or other study-related procedures.

None: The event is not associated with the device or procedure. There is no relation between the event and the device or procedure.

Possibly Related: The temporal sequence between the device or procedure and the event is such that the relationship is not unlikely or there is no contradicting evidence that can reasonably explain the Subject's condition. There is a possibility of any relation between the event and the device or procedure.

Related: The temporal sequence is relevant or the event abates upon device application completion/removal or the event cannot be reasonably explained by the patient's condition or comorbidities. The event is related or most likely associated with the device or procedure.

Unknown: There is no evidence or relevant data available to assess the relationship between the event and the device or procedure.

9.2 Monitoring of Adverse Events

Adverse events (AEs) may be volunteered by Subjects, elicited by Investigator or others, or observed. All AEs will be assessed by the Investigator who will determine whether or not the event is related to the device, and/or insertion or removal procedure or other study-related procedure. The Investigator will determine whether or not the event meets the serious criteria. If it is determined that an AE has occurred, the Investigator should obtain all the information required to complete the reporting process, including source documentation.

9.3 Adverse Event Reporting

All adverse events (AEs) will be reported by the Investigator and reviewed by the Sponsor in compliance with applicable regulations. Site will follow local IRB reporting requirements for reporting to IRB.

All SAEs must be reported to Sponsor as soon as possible but in no event later than 48 hours after learning of the event. Include Study ID, Study Site, Adverse Event, causal relationship to device and procedure (insertion/removal/other study procedure), seriousness, expectedness, and provide source documentation as soon as available. The AE form of the CRF must be completed within 3 working days of awareness for all SAEs.

All UADEs must be reported to the Sponsor and to the reviewing IRB as soon as possible, but in no event later than 48 hours after the Investigator first learns of the event (21 CFR 812.150(a)(1)). The AE form of the CRF must be completed as soon as possible but no later than 3 working days for all UADEs.

All adverse events classified as possibly related or related to the device or procedure will be reported to Senseonics as soon as possible but no later than 3 days of learning of events.

9.3.1 AE Reporting Period

Adverse events are reported from enrollment until study participation has ended. Adverse events will be followed until resolution, AE has stabilized, or the study has been completed.

9.3.2 Pre-existing Medical Conditions

Pre-existing medical conditions or symptoms reported prior to enrollment will not be recorded as an AE. In the event there is a change in the pre-existing medical condition or symptoms due to the device or study-related procedure, than an AE must be recorded.

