2.2 Safety

The safety objective is to demonstrate safety of the Senseonics CGM System through 90 days post-insertion by measuring the incidence of device-related or sensor insertion/removal procedure-related serious adverse events (SAEs) during the investigation. The other safety objectives are to evaluate the incidence of all procedure-related or device-related adverse events (AEs) in clinic and home use, and to evaluate the incidence of all adverse events, regardless of relatedness, in clinic and home use. The safety endpoints and their respective analysis are detailed further in Section 11.2.

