8.2.1 Anticipated Adverse Effects

The following adverse effects could occur in association with insertion, removal, and/or use of the Senseonics CGM System Sensor and/or Transmitter:

- Infection, local or systemic, possibly resulting in sensor removal
- Excessive bleeding during insertion or removal
- Bruising or swelling
- Poor wound healing after insertion or removal
- Keloid and/or scar formation
- Excessive or prolonged pain or discomfort at the Sensor site
- Nerve damage causing tingling, numbness, pain or weakness
- Uncomfortable heating
- Burn
- Electrostatic shock
- Skin irritation and/or redness
- Itch
- Discoloration of skin
- Hematoma formation
- Device migration
- Skin erosion
- Allergic reaction to the device components, local anesthetic, or other medication or materials used in the procedure
- Anxiety and/or nervousness and/or lack of sleep
- Device fragments or particulate matter remaining in the body
- Failure to retrieve device or device left behind
- Difficulty in removing device that may require surgery
- Device malfunctions of the Sensor and/or Transmitter with possible need to remove and/or replace the Sensor and/or Transmitter
- Burning sensation or pain.
- Elevated blood pressure
- Water retention in the tissue, swelling or edema
- Airway spasms

- Shortness of breath
- Circulatory disorders
- Confusion
- Disorientation
- Increased or decreased sensitivity to touch or pain
- Metallic taste
- Sleepiness
- Visual disturbances and/or blurred vision
- Tinnitus
- It is possible that the local anesthetic could cause a reaction other than listed or previously seen.
- Fluid/electrolyte disturbances such as fluid retention
- Muscle weakness
- Osteoporosis
- Peptic ulcer
- Pancreatitis
- Ulcerative esophagitis
- Impaired wound healing
- Headache
- Psychic disturbances and mood swings
- Convulsions
- Glaucoma
- Weight gain
- Nausea and/or vomiting
- Malaise
- Irritability
- Insomnia
- Heartburn
- Hyperglycemia
- Ketosis
- Headaches
- Dizziness, lightheadedness, and/or fainting
- It is possible that the use of the Senseonics CGM system could cause a reaction other than listed or previously seen.
- It has not been determined whether the risks usually associated with injectable dexamethasone apply to the use of dexamethasone elution ring, a highly localized, controlled-release device.
- The dexamethasone ring could cause other adverse events not listed or previously seen.

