11.2 Safety Endpoints

The safety endpoint is the incidence of device-related or insertion/removal procedure-related serious adverse events (SAEs) in the clinic and during home use through 90 days post-insertion.

An Adverse Event is considered 'related' if the relatedness is categorized as 'possibly related', or 'related'. The assessment of seriousness and relatedness made by the Medical Monitor will be used for analysis. The numbers of SAEs and the percentage of patients with SAEs will be reported for each SAE type that is observed, identified as device-related, procedure-related or unrelated to the study (Table 3 in APPENDIX 1). The count and proportion of patients experiencing at least one device-related or procedure-related SAE will be presented. No inferential statistical analysis will be performed.

Other safety endpoints include:

- Incidence of insertion/removal procedure or device-related adverse events in the clinic and during home use.
- Incidence of all adverse events in the clinic and during home use.
- Incidence of hospitalizations due to hypoglycemia, hyperglycemia or ketoacidosis occurring during home use.
- Incidence of reported hypoglycemic and hyperglycemic events occurring during home use.

For each of the adverse event (AE or SAE) categories above, the numbers of AEs and the percentage of patients with AEs will be reported for each AE type that is observed and be stratified by the target age enrollment categories (Tables 4A-4E in APPENDIX 1). A listing (Table 5 in APPENDIX 1) will be prepared that identifies each patient with a reported AE or SAE, and relevant information including date of onset, severity level, seriousness, relatedness to the device or procedure, classification as anticipated or unanticipated, corrective action(s) taken, and resolution status (resolved or ongoing).

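### Section 9.3.2 ties the recording of a worsened pre-existing condition to its cause, which conflicts with the all-AE endpoint for non-serious events

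*Protocol*

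**What the plan says.** Protocol 9.3.2 has two sentences. The first is a general exclusion: "Pre-existing medical conditions or symptoms reported prior to enrollment will not be recorded as an AE". The second is the only exception it states: an AE is required where there is a "change in the pre-existing medical condition or symptoms due to the device or study-related procedure, than an AE must be recorded". Nothing is said about a worsening with another cause.

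Elsewhere the plan does not make an AE depend on cause:

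- Protocol 9.1 defines an AE as any untoward medical occurrence, "whether or not related to the investigational medical device".
- Protocol 9.3 states: "All adverse events (AEs) will be reported by the Investigator and reviewed by the Sponsor in compliance with applicable regulations".
- Protocol 2.2 sets an objective "to evaluate the incidence of all adverse events, regardless of relatedness, in clinic and home use". SAP 4.1.2 repeats it.
- Protocol 11.2 lists the endpoint "Incidence of all adverse events in the clinic and during home use". SAP 6.8 repeats it.

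On causality, the investigator assesses each event (protocol 9.2). For the safety analysis, however, "The assessment of seriousness and relatedness made by the Medical Monitor will be used for analysis" (protocol 11.2). The same section counts an event graded possibly related as related.

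**The concern.** A general exclusion with one causal exception is naturally read as leaving out everything else. If every worsening were recordable, the causal qualifier in 9.3.2 would have no purpose. A site that follows 9.3.2 would therefore not record a non-serious worsening that it attributes to something other than the device or a study procedure.

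Two summaries are at stake. The all-AE summary is meant to ignore causality, so a causal filter at collection defeats its purpose. The related-AE summary is exposed because the filter is stricter than the analysis threshold: a change that is possibly, but not clearly, caused by the device may not count as due to it, and so may go unrecorded.

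The matter has some substance here. Protocol 8.2.5 says it is not yet known whether the risks of injectable dexamethasone apply to the eluting ring. Section 8.2.1 lists effects, such as "Elevated blood pressure", glaucoma and osteoporosis, that could appear as worsening of a condition already present. Subjects with such conditions can enter: exclusion criterion 5 bars only uncontrolled hypertension, and SAP Table 24 plans a row for hypertension medication.

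**Working it through.** The documents state no AE rate, event count or precision target on this point, so there is no figure of the plan's own to reproduce. The check compares the rules and then gives a scale.

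**Order of steps.** The causality scale in 9.1 includes the grades None and Unknown. Those grades are needed only if events are recorded before causality is settled. Sections 9.1, 9.2, 9.3 and 11.2 thus describe one sequence: record, grade at the site, adjudicate, analyse. Section 9.3.2 reverses it for pre-existing conditions, because the causal judgement has to be made before there is an AE to record. The SAP repeats the endpoint and adds no collection rule that resolves the conflict.

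**Threshold.** Section 9.1 treats an event as possibly related when a relationship is not unlikely, or when nothing contradicting it reasonably explains the subject's condition. Section 11.2 counts that grade as related. The wording of 9.3.2 asks for a change caused by the device or procedure, which is a higher bar.

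**Serious events.** Section 9.3 requires every SAE to be reported to the sponsor within 48 hours, with no condition on relatedness. The note to the SAE definition in 9.1 exempts only a planned hospitalization for a pre-existing condition, or a procedure the plan requires, without serious deterioration. The better reading is that serious worsening stays reportable whatever its cause.

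**Scale.** Inputs: 36 inserted subjects (protocol 11.3.2.2), and a safety population of all subjects who undergo insertion (11.1.6). If k subjects have an unrecorded worsening and no other recorded AE, the percentage of subjects with an AE falls by 100 × k/36:

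| k | Fall in subject percentage (points) |
|---|---|
| 1 | 2.78 |
| 2 | 5.56 |
| 3 | 8.33 |
| 5 | 13.89 |

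Let p be the proportion of subjects with a non-serious worsening judged unrelated. This is an assumption, since the documents give no value. The expected number of such subjects is 36p. If subjects are independent, the chance of at least one is 1 − (1 − p)^36:

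| Assumed p | Expected subjects | Chance of at least one |
|---|---|---|
| 2% | 0.7 | 52% |
| 5% | 1.8 | 84% |
| 10% | 3.6 | 98% |
| 20% | 7.2 | >99.9% |

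The second table counts affected subjects, not percentage points lost. A subject with any other recorded AE stays in the numerator, so the loss in the subject percentage runs from zero up to 100 × p points. The event count, which 11.2 also reports, falls in either case.

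**The case against.** The strongest reply is that 9.3.2 never says *only*. It states when a change must be recorded and does not forbid recording others. Its exclusion can be read as covering the baseline state alone, with 9.1 and 9.3 still requiring everything else. This is a possible reading, and it means that under-recording is not certain. It does not remove the defect. A study at up to 4 sites would then have a rule that each site may apply differently, on an endpoint that is a simple count.

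A reader might infer that even an unplanned hospitalization for a worsened condition would go unrecorded, and that the main endpoint of related SAEs would lose events. The documents do not support this, because the SAE rules in 9.1 and 9.3 carry no relatedness filter. A little ambiguity remains: an SAE is defined as a kind of AE, and 9.3.3 has an explicit exception for serious events that 9.3.2 lacks. That is a reason to tidy the wording, not evidence that serious events are lost.

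A reader might also infer that the Medical Monitor would never see the missing events. That is too strong. Section 13.13 gives the Monitor clinical data, subject safety data and laboratory values to review. Subjects are told to report new medications, hospitalizations and significant medical changes (4.2.6), and entered data are reviewed to identify and query AEs (section 10.1). These routes may bring an event to light but do not guarantee it. Adjudication of relatedness works on events recorded as AEs.

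Finally, the affected endpoints are descriptive, with no hypothesis attached. That limits the consequence, but a descriptive incidence still depends on complete collection.

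**Conclusion.** The point holds for non-serious events. As written, 9.3.2 conflicts with the AE definition, the reporting rule and the all-AE endpoint, and it puts the site's causality judgement ahead of the Monitor's. The likely effect is under-counting, or inconsistent recording between sites, of non-serious AEs in the all-AE and related-AE summaries. The main SAE endpoint is much less exposed.

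The size cannot be fixed from the documents. The 2.8 points per subject applies only to a subject with no other recorded AE, and the range of p is an assumption made for scale. It would be wrong to turn an assumed rate of, say, 5% to 20% into a loss of 5 to 20 points. Those figures are upper bounds that require every affected subject to have no other AE and every site to take the restrictive reading.

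**What to change.** Reword 9.3.2 to say that a condition or symptom present at enrollment is not an AE in its baseline state, but that any worsening in severity, frequency or nature after enrollment is recorded as an AE whatever the suspected cause. Relatedness is then graded under 9.1 and adjudicated by the Medical Monitor. Repeat the rule in the CRF completion guideline so that all sites apply it alike. Leave the separate handling of glucose excursions in 8.2.3 and 9.3.3 unchanged.

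The cost is one reworded rule, a guideline note, a few more AE forms, and a slightly higher all-AE percentage. The change is best made before data collection, because events that were never recorded are hard to recover afterwards.

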9.3.3 Protocol-Specific Reporting Information

For the purpose of this protocol, mild (i.e., clinically non-significant) hypoglycemia and hyperglycemia symptoms or blood glucose values out of the normal range will not be reported as adverse events unless determined to meet the criteria of a Serious Adverse Event.

